We propose a randomized trial of a multifaceted intervention designed to optimize a patient-centered approach for improving adherence to prescription opioids, “Improving the Safety of Opioid Prescriptions (ISOT).” Primary care clinicians and PACT (Patient Aligned Care Team) nurses will be randomized to ISOT or the control condition; patients will be nested by clinician status. Clinicians and PACT nurses in both groups will participate in an interactive workshop on reducing prescription opioid abuse and enhancing safety. In addition, clinicians assigned to ISOT will work with a nurse care manager (NCM) who will maintain a registry of enrolled patients, track UDT administrations and results, examine state Prescription Drug Monitoring Program data, monitor medical records, and collaborate with an internist and substance abuse specialist to provide decision support when patients demonstrate evidence of prescription opioid misuse or abuse. The NCM will also meet with intervention patients to discuss strategies for reducing opioid adverse effects and preventing diversion, and to provide rationale for prescription opioid adherence monitoring. Thus, our intervention targets system, clinician, and patient levels. A research goal is to enhance patient-centered pain care and improve the quality of the communication and relationship between the patient and the primary care team pertaining to this challenging topic. The main objectives of this study are to evaluate the efficacy and acceptability of a multifaceted intervention (ISOT) to enhance opioid safety in patients with chronic pain.

SPECIFIC AIMS

Aim 1: Evaluate to what extent a multifaceted intervention (ISOT) enhances prescription opioid safety.

Hypothesis 1: At 12 months, ISOT patients will have lower rates of prescription opioid abuse, as assessed via multiple methods (self-report, clinical interview, urine drug testing), compared to patients of clinicians randomized to the control condition.

Hypothesis 2: At 12 months, ISOT patients will experience fewer adverse events (defined in this proposal to include emergency room visits, overdoses, falls, motor vehicle accidents).

Aim 2: Assess to what extent assignment to ISOT impacts pain treatment-related processes of care.

Hypothesis 1: ISOT patients will have more modifications to clinical care documented in the medical record, including more frequent UDTs and queries to state prescription drug

monitoring programs.

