Measures of Prescription Opioid Misuse/Abuse (Aim 1): The primary outcome will be responses to the Current Opioid Misuse Measure (COMM), a 17-item self-report measure that assess several constructs that place individuals at risk of opioid misuse and abuse.⁸⁰ The COMM has been well-validated⁸¹ and previously used in treatment outcome studies.³³ The COMM has also been validated for detecting prescription opioid abuse using cut-off scores ≥ 13 .⁸² The Timeline Followback (TLFB; Sobell & Sobell, 1992) is a frequently used assessment method that uses calendar prompts to elicit frequency and intensity of substance use within a specific timeframe. The TLFB has demonstrated good test-retest reliability and validity for assessing multiple substances at one time (Ehrman & Robbins, 1994; Fals-Stewart et al., 2000). This study will assess use of alcohol, marijuana, methamphetamine, cocaine, heroin, opioid medications, and other prescription medications in the past 30 days. The Structured Clinical Interview for DSM-IV(SCID) will be used to assess current alcohol and substance use disorders.⁸³ The Overdose Risk Behavior (ORB) questionnaire is a newly-developed 14-item self-report measure that assesses behaviors and activities that place an individual at higher risk of accidental overdose to prescription opioids. Participants will complete Urine Drug Tests, to evaluate for the presence of substances ingested by participants. UDTs will evaluate for cannabis, cocaine, amphetamines, benzodiazepines, barbiturates, opioids, and opiates. Confirmatory testing will be conducted for all UDT screens with unexpected results. The purpose of UDT is to have confirmation of certain prescribed and illicit substances that have been ingested by study participants. Research staff will review medical record data prior to research visits to confirm medication status. Participants will be asked to validate pharmacy data about prescription status, as well as medications prescribed outside VA.

Measures of Opioid-Related Adverse Events (Aim 1): Prior to appointments, research staff will review medical record data for participants to track adverse effects. This includes emergency room visits, falls, and overdoses. Participants will also be queried about these effects and motor vehicle accidents at each research visit.

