Aim 1: Evaluate to what extent a multifaceted intervention (ISOT) enhances prescription opioid safety. For Aim 1, we use 8.9 as an estimated standard deviation (SD) for change in COMM score from baseline to 12 months.⁹⁵ This SD estimate is based on SD's in prior intervention research.³³ For each group, an estimated SD for change was obtained using the two SD's and a within-subject intraclass correlation coefficient of 0.5. Averaging the corresponding variances leads to an estimated variance of 78 (SD=8.9). Power calculations were performed based on 28 or 32 (we may recruit as many as 40 PCPs, but do not anticipate that many will consent to participate) clinicians per intervention group and 4 or 5 patients per clinician. Table 1 displays differences in mean COMM change that can be detected under various values for the intraclass correlation coefficient. Our targeted sample size is 32 PCPs per group and an average of 5 patients per PCP. With a loss of 4 PCPs per group and 1 patient per PCP, we have power to detect small differences (able to detect $< \frac{1}{2}$ SD change) in COMM score. For Aim 1, we plan to conduct analyses for self-report data (COMM), clinical interviews to assess current substance use disorders (SCID), and results from research-administered UDTs. With n=320, 28-32 PCPs per group, and 4-5 patients per PCP, we have statistical power greater than 80% to detect differences in percentages between groups of about 20% for binary outcomes from the SCID and UDT (see Table 2 below for similar calculations for Aim 2).

Table 1. Mean differences in COMM change from baseline to 12 months (80% power, $\alpha=0.05$).

Intra-class correlation	Mean detectable difference in COMM change, n=4 patients per clinician, 28 clinicians per intervention	Mean detectable difference in COMM change, n=4 patients per clinician, 32 clinicians per intervention	Mean detectable difference in COMM change, n=5 patients per clinician, 28 clinicians per intervention	Mean detectable difference in COMM change, n=5 patients per clinician, 32 clinicians per intervention
0	3.4	3.2	3.0	2.8
0.02	3.5	3.3	3.2	2.9
0.04	3.6	3.4	3.3	3.1
0.10	3.9	3.6	3.6	3.4

Analyses for Aim 1: For comparison of mean COMM change between groups, we will use mixed longitudinal models with a random effect for PCP and patient, to allow for correlation between

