observations on different patients of the same PCP and for repeat observations on the same patient. Transformations of the outcome will be applied to meet distributional assumptions. In linear mixed models, we will include baseline measures of patient age, sex, depressive symptoms, history of SUD, and pain severity as covariates. We will also adjust for baseline COMM score and the stratification variables: PCP training type (MD/DO vs NP or PA) and proportion of clinician panel prescribed opioids (high vs low). In addition to testing formal hypotheses, we will report 95% confidence intervals for the differences in mean outcomes between groups at 6 and 12 months. For comparing the percentages classified as abusing opioids at any time during follow-up (combining information from 6 and 12 months) based on SCID and UDT, we will use generalized-linear mixed models (or GEE as needed) to incorporate correlation between patients of the same PCP. We will adjust for baseline measures of the outcome along with the covariates listed above. We will report group comparisons on all three primary outcomes (COMM, SCID, and UDT). Assuming 15% of the sample has current SUD (consistent with other research), we will not conduct interaction analyses, but will present descriptive information for each outcome (COMM, SCID, UDT) on treatment outcomes by SUD status.

Data on opioid-related adverse events will be obtained from the medical record and participant self-report. We will collect data on opioid overdoses, falls, motor vehicle accidents, and ER visits related to pain. Descriptive information on opioid-related events will be provided for each group (numbers and percentages of participants with each event). Because the number of adverse events is expected to be small, we will use Fisher's Exact test to compare adverse event percentages between groups. We will compare both percentages for each individual type of event as well as percentages of individuals experiencing any adverse event between groups.

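### The plan names COMM as the only primary outcome in one place and COMM, SCID and UDT as three primary outcomes in another, and states no rule for which result decides Hypothesis 1

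*Combined protocol and SAP*

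**What the plan says.** **Which outcome is primary.** Study Measures (Measures of Prescription Opioid Misuse/Abuse, Aim 1) uses the singular: "The primary outcome will be responses to the Current Opioid Misuse Measure (COMM), a 17-item self-report measure". Data Analysis (Analyses for Aim 1) uses the plural: "We will report group comparisons on all three primary outcomes (COMM, SCID, and UDT").

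**The hypothesis.** Specific Aims, Aim 1, Hypothesis 1 reads "At 12 months, ISOT patients will have lower rates of prescription opioid abuse, as assessed via multiple methods". It lists self-report, interview and urine testing without ranking them.

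**Time frame.** Table 1 is titled "Mean differences in COMM change from baseline to 12 months", which agrees with the hypothesis. The COMM model is longitudinal, with confidence intervals promised at both 6 and 12 months. SCID and UDT are compared as abuse "at any time during follow-up (combining information from 6 and 12 months) based on SCID and UDT".

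**Power.** COMM has its own table at 80% power and alpha 0.05. For the other two, Data Analysis (Aim 1) claims more than 80% power for "differences in percentages between groups of about 20% for binary outcomes from the SCID and UDT". That sentence states no alpha and refers to Table 2 for similar calculations.

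**Scale.** The hypothesis is about rates. COMM is powered and tested as a mean change. Study Measures says "The COMM has also been validated for detecting prescription opioid abuse using cut-off scores" of 13 or more, but no planned test uses that cut-off. SCID and UDT are analysed as percentages.

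**The concern.** Both statements about the primary outcome are current text, and they cannot both be true. Nothing else in the plan settles the matter by rule: there is no testing order, no split of alpha, and no statement that one positive result suffices or that all three are needed.

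The three measures are a questionnaire, an interview and a laboratory test, so they may well disagree. If COMM improves and UDT does not, Study Measures reads as a success and Analyses for Aim 1 offers no reading. If SCID or UDT differs when 6 and 12 months are pooled but not at 12 months, the planned comparison and the hypothesis point to different answers. For COMM, the deciding contrast in the longitudinal model (6 months, 12 months or overall) is not named. In each case the interpretation could be chosen after the results are known.

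**Working it through.** **1. Does Table 1 reproduce, and for what test?**
Inputs from Data Analysis, Aim 1: SD of COMM change 8.9; k = 28 or 32 clinicians per arm; m = 4 or 5 patients per clinician; ICC 0 to 0.10; 80% power; alpha 0.05 (two-sided is my assumption).

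SE = 8.9 × √[2(1 + (m−1)ICC)/(km)], and detectable difference = (t(1−α/2) + t(0.80)) × SE with 2k−2 df.

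- 32 × 5, ICC 0.02: SE = 8.9 × √(2 × 1.08/160) = 1.034; (1.999 + 0.847) × 1.034 = 2.94. Table 1 gives 2.9.
- 28 × 4, ICC 0.10: SE = 8.9 × √(2 × 1.30/112) = 1.356; (2.005 + 0.848) × 1.356 = 3.87. Table 1 gives 3.9.

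All 16 cells agree to rounding. Table 1 is therefore correct for one COMM test at two-sided 0.05, with no allowance for other primary tests.

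**2. What would each possible decision rule imply?**

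*COMM alone decides.* The chance of a false claim of benefit is 2.5%, and Table 1 stands.

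*Any one of three decides, each at two-sided 0.05.* If the tests are independent, the chance of at least one false result in the direction of benefit is 1 − 0.975³ = 7.3%. For equally correlated normal statistics (correlations assumed; the plan gives none):

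| Assumed correlation | False claim of benefit |
|---|---|
| 0 | 7.3% |
| 0.5 | 6.3% |
| 0.7 | 5.5% |
| 0.9 | 4.2% |

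*All three are required.* There is no inflation, but joint power cannot exceed that of the weakest test. If each had 80% power and they were independent, joint power would be 0.8³ = 51%.

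**3. What would keeping three primaries cost COMM?**
Under Bonferroni each test has 0.05/3 = 0.0167.

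- With the unadjusted change SD of 8.9 (32 × 5, ICC 0.02), the detectable difference becomes (2.461 + 0.847) × 1.034 = 3.42. Power at 2.94 falls from 80% to about 65% (noncentral t, 62 df), and the other cells give the same 65%.
- The planned model adjusts for baseline COMM. With the plan's within-subject correlation of 0.5, and assuming equal SDs at both times and the same ICC, the residual variance is (1 + 0.5)/2 = 0.75 of the change variance, so SD = 8.9 × √0.75 = 7.71. The detectable difference at 0.0167 is then 2.96, and power at 2.94 is about 79%. The same adjusted model at 0.05 would have about 90%.

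A price remains, but the planned adjustment roughly restores the power that Table 1 advertises.

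**The case against.** The strongest reply is that the plan, read as a whole, already points to COMM at 12 months. Study Measures names one primary outcome, the hypothesis gives 12 months, and COMM alone has its own Aim 1 power table, for change to 12 months. On this view the sentence in Analyses for Aim 1 is a promise to report, with one loose label. Much of this stands: the gap in timing is narrow, and the promise to report all three means no result is concealed. What the reply does not supply is a rule. The plural label is in the section that governs the analysis, and the unranked hypothesis fits it at least as well as the singular one.

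Four stronger readings are tempting, and the documents do not support them.

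- *The error rate is inflated.* That holds only under an any-one rule, which the plan does not state. A figure of 14.3% (1 − 0.95³) also counts false findings of harm.
- *Three primaries would break the plan's claim that* "With a loss of 4 PCPs per group and 1 patient per PCP, we have power to detect small differences", *under half an SD.* At 0.0167 one cell of 16 (28 × 4, ICC 0.10) gives 4.50 against 8.9/2 = 4.45, but only with the unadjusted SD. With baseline adjustment, on the assumptions above, it is about 3.90.
- *SCID and UDT are underpowered.* The plan gives no control-arm rate for either. Its 15% figure for current substance use disorder describes the sample and explains why interactions are not tested.
- *Abuse rates go untested.* SCID and UDT are compared as percentages. The mismatch between rates and means is confined to COMM.

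**Conclusion.** The contradiction is real and should be resolved before group comparisons are seen, because it concerns what decides the trial's main hypothesis. It has two parts: one primary outcome against three with no decision rule; and a 12-month hypothesis against an any-time comparison for SCID and UDT, with the deciding COMM contrast unnamed.

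Its numerical size depends on a rule the plan does not state: no inflation if COMM alone decides or if all three are required, and 2.5% rising to about 4–7% if any one suffices. Those figures rest on assumed equal correlations from 0.9 down to 0 and two-sided tests. Table 1 itself is not in error.

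The title page describes this text as the original analysis plan from the funded proposal and refers to a publication for the final protocol. Whether the conflict persisted cannot be told from these documents.

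**What to change.** Before group comparisons are seen:

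1. In Analyses for Aim 1, state that the primary test is the difference between arms in mean COMM change from baseline to month 12, at two-sided 0.05. This agrees with Study Measures and leaves Table 1 unchanged. Label SCID and research UDT as secondary.
2. Give SCID and UDT one time frame that agrees with Hypothesis 1, for example 12 months, with the any-time comparison as supportive.
3. Add to Hypothesis 1 that mean COMM change is its primary test and that SCID and UDT abuse rates are its secondary tests. Abuse rates need not be removed from the hypothesis.

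This costs text and no new data, but it is also a change of substance. The primary claim would rest on self-report, and the research UDT, the one laboratory measure, would become secondary.

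If the sponsor prefers three primaries, the plan should state the decision rule and one time frame. Under an any-one rule, use Holm. Holm has no single adjusted alpha, so 0.0167 is only its Bonferroni floor. There, COMM power at the Table 1 differences is about 65% with the unadjusted SD, or about 79% with the planned baseline adjustment (correlation 0.5, equal SDs assumed). Under an all-three rule no adjustment is needed, but joint power is capped by the weakest test.

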- a. The NCM will maintain a registry of all enrolled patients and track UDT administrations. For patients that have not been administered a UDT in 12 months or more, the NCM may assist the PCP by placing an order for UDT in the medical record.
- b. The NCM may write the UDT order for the PCP to sign, if requested. The NCM will recommend checking state PDMP data for patients without a past-year check. (In Oregon, only prescribers are authorized to check PDMP data, so the NCM could not query the database him/herself.) PDMP checks are recorded in the medical record, so the research team will be able to track frequencies. If requested, the NCM may collaborate with pharmacy services to query state PDMP databases.
- c. The NCM will provide support about methods for talking with patients about prescription opioid adherence monitoring. This will include providing written information, such as scripts that clinicians can follow. In pilot interviews, PCPs requested these types of materials to assist with improving adherence to opioid regimens.
- d. The NCM will track all UDTs, notify the PCP of the results, and provide recommendations

about potential next steps in care. With collaboration from the primary care pain specialist and substance abuse specialist, the NCM will provide decision support to clinicians for patients with prescription opioid abuse about options for modifying treatment. The NCM will also follow-up to ensure treatment recommendations are implemented.

- e. With input from the NCM, some patients may be referred for supplemental treatment. This may include referral to the substance abuse treatment program, mental health clinic, or specialty pain service.
- f. The NCM may identify potential side effects or risky prescribing practices that have not been addressed.

Follow-up: Participants will complete assessments at baseline, 6 months, and 12 months post-baseline. During research visits, participants will complete all study measures, the structured clinical interview, and provide a UDT.

In the course of the study, a PCP or PACT nurse who is enrolled in the study may leave their position at the Portland VA. Clinical patients who are “attached” with these clinicians and already enrolled in the study will remain eligible to participate. Clinical recommendations that are made regarding patient’s care will continue to be forwarded to PACT team members who remain involved in each patient’s treatment.

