Before analyses are conducted, data will be audited for quality, including missing data patterns and evaluation of distributions with reference to planned models. The evaluation of distributions includes the detection of outliers and checking distributions of variables to ensure they meet the assumptions of planned analyses. Power calculations (below) are based on comparisons that account for data clustering. The analyses will incorporate covariate information, in particular baseline data on age, gender, depressive symptoms, history of substance use disorder (SUD), and pain intensity, which will enhance power. Analyses will be conducted with all enrolled participants regardless of attrition (intent-to-treat).

Management of Missing Data: The pattern of missingness will be examined and baseline responses compared between those with and without missing data. Variables related to missingness will be included in the analyses which should yield valid inferences.⁹⁴ We will complete sensitivity analyses comparing the main analyses results with results from analyses with completers only and based on multiple imputation.

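### The only test of fewer adverse events (Aim 1, Hypothesis 2) uses neither baseline event history nor PCP clustering; the any-event composite should move to the model planned for SCID and UDT

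*Combined protocol and SAP*

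**What the plan says.** - **Hypothesis.** Specific Aims, Aim 1, Hypothesis 2 states that at 12 months "ISOT patients will experience fewer adverse events", counting emergency room visits, overdoses, falls and motor vehicle accidents.
- **Test.** Data Analysis, Analyses for Aim 1: "Because the number of adverse events is expected to be small", "we will use Fisher's Exact test to compare adverse event percentages between groups". The test is applied to each event type and to "percentages of individuals experiencing any adverse event between groups". No other comparison of these events is planned, and no expected rate or power is given.
- **Baseline data.** Study Measures (opioid-related adverse events): "Prior to appointments, research staff will review medical record data for participants to track adverse effects", and "Participants will also be queried about these effects and motor vehicle accidents at each research visit". The second Follow-up paragraph, after the intervention components, makes baseline one of those visits: "Participants will complete assessments at baseline, 6 months, and 12 months post-baseline". No look-back period is stated.
- **General rule.** The opening of Data Analysis says: "The analyses will incorporate covariate information, in particular baseline data on age, gender, depressive symptoms" (the list goes on to SUD history and pain intensity), with the aim of raising power.
- **The other binary Aim 1 outcomes.** SCID and UDT are compared by generalized linear mixed model, or GEE if needed, allowing for correlation within PCP and adjusting for the baseline value of the outcome and the listed covariates.

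**The concern.** Of the Aim 1 comparisons, only the adverse-event one drops both features that the plan uses elsewhere: adjustment for the patient's own baseline value and allowance for PCP clustering. A patient with earlier falls or ER visits may well be likelier to have them again. If so, a chance imbalance in history stays in the result and some precision is given up. PCPs are the unit of randomisation, so a test that treats patients as independent can also have a type I error above its nominal level.

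The stated reason, few events, suits overdoses and motor vehicle accidents. It is less clearly right for the any-event composite, which is at least as frequent as its commonest component. The documents give no rate that shows the composite to be too rare to model.

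**Working it through.** **1. The plan's nearest figure.** No power is stated for adverse events. Table 2 (UDT ordering, 40% control rate) shows the plan's method for binary outcomes: a two-sided two-proportion test at 0.05, with effective n per arm = mk / [1 + (m - 1) x ICC]. Take 4 patients x 28 PCPs at ICC 0.10, where Table 2 gives 61%:

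- n = 112 / 1.3 = 86.2; mean proportion 0.505
- z = (0.21 x sqrt(86.2) - 1.96 x sqrt(2 x 0.505 x 0.495)) / sqrt(0.40 x 0.60 + 0.61 x 0.39) = (1.949 - 1.386) / 0.691 = 0.815
- power = 0.79

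All 16 cells agree within about 0.4 points. So the plan allows for clustering when it powers binary outcomes, but not when it tests adverse events.

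**2. Simulation inputs.** From the plan: 32 PCPs x 5 patients = 160 per arm, alpha 0.05, and ICC between 0 and 0.10. Assumed, because the plan gives no values for events:

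- event rates of 20% vs 9%, 40% vs 25% and 5% vs 1%
- baseline prevalence equal to the control rate
- baseline-to-follow-up odds ratio (OR) of 3 or 6
- stratum odds ratio of 1.5

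The ICC is on the logit scale: a PCP SD of 0.605 gives 0.366 / (0.366 + 3.290) = 0.10. The stand-in for the clustered model is a risk-difference regression with PCP-robust standard errors. There were 3,000 runs per row, so the Monte Carlo standard error is sqrt(0.8 x 0.2 / 3000) = 0.007 for power near 0.8.

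**3. Power for a composite that is not rare.**

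| Rates | OR | ICC | Fisher | Clustered, unadjusted | Clustered + baseline event + strata | Net vs Fisher (points) |
|---|---|---|---|---|---|---|
| 20 vs 9 | 3 | 0 | 0.767 | 0.796 | 0.810 | +4.3 |
| 20 vs 9 | 6 | 0 | 0.766 | 0.790 | 0.832 | +6.6 |
| 40 vs 25 | 3 | 0 | 0.792 | 0.809 | 0.838 | +4.6 |
| 40 vs 25 | 6 | 0 | 0.790 | 0.808 | 0.874 | +8.4 |
| 20 vs 9 | 3 | 0.10 | 0.768 | 0.753 | 0.754 | -1.4 |
| 20 vs 9 | 6 | 0.10 | 0.777 | 0.761 | 0.788 | +1.1 |
| 40 vs 25 | 3 | 0.10 | 0.770 | 0.714 | 0.735 | -3.5 |
| 40 vs 25 | 6 | 0.10 | 0.766 | 0.729 | 0.780 | +1.4 |

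At ICC 0.02 (2,000 runs, baseline event only), Fisher against the clustered adjusted model gave 0.75 to 0.80 and 0.76 to 0.83 at 20 vs 9, and 0.79 to 0.83 and 0.79 to 0.86 at 40 vs 25: +4 to +7 points. A further set of runs at ICC 0.10 put the net change at about -1 to +5. The two sets at ICC 0.10 agree only that the change is near zero.

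**4. Separating the sources of the gain.** In a patient-level model at ICC 0, adding only the baseline event gives:

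- 20 vs 9: 0.810 to 0.823 (OR 3) and 0.805 to 0.842 (OR 6)
- 40 vs 25: 0.827 to 0.850 (OR 3) and 0.822 to 0.885 (OR 6)

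That is +1.3 to +6.3 points. Adding only the strata gives 0.1-0.2 points. The rest of the gap at ICC 0 is Fisher's conservatism.

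**5. Type I error (baseline OR 3).** Fisher: 0.036 (20% rate) and 0.037 (40%) at ICC 0; 0.055 and 0.062 at ICC 0.10. A further set of runs gave about 6-7%. The standard error is sqrt(0.05 x 0.95 / 3000) = 0.004, so 0.055 alone is within noise and 0.062 is not. The clustered adjusted model gave 0.047-0.051 throughout. The ICC 0.10 rows in step 3 therefore flatter Fisher.

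**6. Rare events.** At 5% vs 1% the expected counts are 160 x 0.05 = 8 and 160 x 0.01 = 1.6. At ICC 0 the baseline term moves the patient-level model from 0.584 to 0.589 (OR 3) and from 0.583 to 0.598 (OR 6). In the clustered model, power falls slightly with both terms added (0.593 to 0.579 and 0.593 to 0.584). An adjusted logistic Wald test has about 0.30 power against Fisher's 0.43.

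**The case against.** The plan gives a reason for Fisher's test, and for rare event types that reason holds: step 6 shows that an adjusted logistic model can do worse. The Aim 1 analysis also narrows ER visits to those related to pain, so even the composite may be less frequent than its name suggests. The general sentence on covariates lists patient characteristics; it does not promise adjustment for the baseline outcome in every test. All of this stands, and it limits the point to the composite and to single event types that prove common enough to model.

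Several stronger readings are tempting but not supported:

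- **A large, certain loss of power.** The plan uses a within-subject correlation of 0.5 for COMM change. A reader might put it into power = Phi(2.80 / sqrt(1 - 0.5^2) - 1.96) = 0.90 and conclude that 80% becomes 90%. That formula is for a continuous outcome. For a yes/no event, a correlation of 0.5 implies an odds ratio of about 10.5 at 30% prevalence and 13.5 at 20%, and nothing in the documents supports so strong an association.
- **Omitting the strata costs power.** It costs about 0.2 points or less, even with an assumed stratum odds ratio of 1.5.
- **The baseline report predates randomisation.** The Randomization section has PCPs assigned before patients are recruited, so the baseline query comes after assignment of the PCP.
- **The covariate is ready to use.** Events are queried at baseline, but without a stated look-back period the yes/no history is not yet defined.

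**Conclusion.** The point holds in a limited form. Fisher's exact test, as the sole test of Hypothesis 2, ignores baseline event history that the study collects and ignores clustering that the plan models for SCID and UDT. For a composite with 20-40% event rates and baseline odds ratios of 3-6, the baseline term is worth about 1-6 points of power. The net change against Fisher is about +4 to +9 points at ICC 0-0.02. At ICC 0.10 it is near zero, between -4 and +5 over both sets of runs, and the case there rests on validity rather than power, because Fisher's type I error rises to about 6-7%. For rare events the baseline term is worth about 1 point, with no dependable gain. Rates, baseline association and the ICC for events are all assumptions, and the simulated model stands in for the GLMM/GEE. This is a modest, worthwhile improvement and not a flaw that undermines the trial.

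**What to change.** In Analyses for Aim 1:

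1. Make the Hypothesis 2 test the any-adverse-event comparison, using the GLMM/GEE with PCP correlation already planned for SCID and UDT.
2. Adjust it for any such event before baseline (yes/no) and, for consistency with the other models rather than for power, for the two stratification variables.
3. Define one fixed look-back period for the baseline query and chart review, and use the same event definitions before and after baseline. Settle whether all ER visits count or only pain-related ones, since the hypothesis and the analysis text differ.
4. Fix in advance an event frequency below which an event type gets Fisher's exact test or descriptive reporting only. Apply the same rule to the composite.

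The cost is SAP wording, one more model fit, and the need to commit to a threshold and a look-back period. If baseline interviews have already used varying recall periods, chart data may be needed to build the yes/no history. Motor vehicle accidents are not among the events listed for chart review, so for them the history would rest on self-report.
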